Objectives	 Characterize the incidence and prevalence of sequelae of SARS-CoV-2 infection. Characterize the spectrum of clinical symptoms, subclinical organ dysfunction, natural history, and distinct phenotypes identified as sequelae of SARS-CoV-2 infection. Define the biological mechanisms underlying pathogenesis of the sequelae of SARS-CoV-2 infection. 	
Methodology	Ambi-directional longitudinal meta-cohort study (combined retrospective and prospective) with nested case-control studies.	
Endpoint	Primary Endpoints: Presence of candidate PASC symptoms over time (incidence and prevalence). Secondary Endpoints: Biological and recovery trajectories from SARS-CoV-2 infection; organ injury; incident clinical disease.	
Study Duration	Four years	
Subject Duration	Up to four years	

Title	NIH RECOVER: A Multi-site Observational Study of Post-Acute Sequelae of SARS-CoV-2 Infection in Adults	
Population	Infected: Individuals at least 18 years of age meet WHO criteria for suspected, probable or confirmed SARS-CoV-2 infection on or after January 1, 2020.	
	Uninfected: Individuals at least 18 years of age who have never met any of the WHO criteria for suspected, probable or confirmed SARS-CoV-2 infection.	
Number of subjects	12,200 total subjects with SARS-CoV-2 infection and 2,680 total subjects without SARS-CoV-2 infection.	
Statistical Analysis	A flexible study design is proposed to allow modifications to PASC case definition, tiered phenotyping assessments, comparator groups, and/or statistical plan after its initiation to optimize public health impact without undermining validity and integrity of study findings. Modifications in study design may be based on analyses of structured cohort data, unstructured cohort EHR data, and other cohort EHR data.	

2 Key Roles

Principal Investigators Clinical Science Core [name] MS
Helen L. and Martin S. Kimmel Professor of
Advanced Cardiac Therapeutics
Director Heart Failure Programs
NYU Grossman School of Medicine
Leon H. Charney Division of Cardiology
[name]
New York, NY 10016
[contact]

[name]
Professor and Director, Division of Biostatistics
Department of Population Health
NYU Grossman School of Medicine
[name]
New York, NY 10016
[contact]

[name], MHS
Professor, Department of Population Health at
NYU Grossman School of Medicine
Professor, Department of Medicine at NYU
Grossman School of Medicine
Director, Center for Healthcare Innovation and
Delivery Science

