All relevant symptoms are described in the corresponding procedure's SOP. As the symptoms that are most relevant to PASC are better understood, RECOVER's subject matter experts refine the list of relevant symptoms for each test. Once the target sample size (see Section 12.2) has been reached with adequate data quality within each bucket, we cease assigning the test to people in that bucket. This ensures that our total enrollment and procedure sample sizes are as small as can be in order to ensure usable data. In other words, this approach allows us to minimize the number of people that we ask to undergo each test and the risk of the study, while maintaining adequate statistical power.

We anticipate that approximately 30% of participants will undergo each Tier 2 test and a maximum of 20% of participants will undergo each Tier 3 test. For Tier 2 testing, a random sample of 5.6% of SARS-CoV-2 infected and 11.4% of uninfected participants will be asked to undergo each Tier 2 test. These percentages may be modified to ensure the correct distribution of PASC and control participants as testing accrues. In addition, some or all participants who meet test-specific clinical criteria set by subject matter experts will be offered the test so that we ensure an adequate number of participants likely to have a positive test for statistical analysis (see Appendix 5: Tier 2 and 3 eligibility, exclusion criteria for additional description of this process). Among the eligible participants, REDCap will assign some or all of those that meet clinical oversample eligibility criteria to the test (at adaptive proportions designed to keep the total number of participants assigned to the test at not more than 30%) and will randomly assign the test to some of the remainder as described above. As RECOVER follows an adaptive study design, the relevant symptoms for each test will be reviewed and updated periodically to ensure the proper proportion and populations are being selected. When relevant symptoms are changed for tests that also allow random assignment, they only affect the proportion of participants with various conditions assigned the test, but do not change the fact that any participant is still eligible and therefore do not change the risk of the study as a whole. Any participant may decline any Tier 2 or Tier 3 test if offered.

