12.2 Sample Size Determination

The following factors were considered in determining the sample size

- Expected frequency of PASC in the SARS-CoV-2 infected population. Population estimates from studies with selection bias currently range from 25-70%; we used 25% as a conservative estimate.
- The desire for the cohort distribution to include a diverse population, with overrepresentation from non-Hispanic Black, Hispanic and Asian populations relative to general population prevalence to account for a higher rate of SARS-CoV-2 infection and PASC in these populations
- The desire to be able to perform subgroup analyses based on characteristics such as age, sex, race/ethnicity, pregnancy, vaccination status and combinations thereof.

Table 7 shows minimal detectable effect sizes for the key study questions both for the full study sample (Tier 1 N=14,880; Tier 2 N=4,464 and Tier 3 N=2,976) and for subgroups of 25% thereof. These sample sizes for Tier 2 and Tier 3 assume that 25% of infected subjects will have abnormal symptoms. It is further assumed that all infected subjects with abnormal symptoms will progress to Tier 2 (N=3,050) and 5.6% of infected subjects without symptoms will progress to Tier 2 (N=512). Among uninfected subjects, 26.8% (N=718) will progress to Tier 2. 68% of infected subjects with abnormal symptoms will progress to Tier 3, and 3.8% of infected subjects without symptoms will progress to Tier 3. Among uninfected subjects, 18.2% will progress to Tier 3. The infected cohort is expected to include 1,867 pregnant individuals and the uninfected cohort is expected to include 583 pregnant individuals.

Table 7: Sample size calculations

					Min detectable ES*	
Tier	Comparison groups		Effect of interest	Assumptions	Full sample	25% subgroup (e.g. inpatients, Hispanic individuals, etc.)
1	Infected	Uninfected	Difference in risk of PASC between infected and uninfected	Risk of PASC in infected: 25%	3.50%	6.80%
1	Infected w/ RF	Infected w/out RF	Risk difference for PASC in infected with RF vs. without RF	Prevalence of RF: 20%, risk of PASC in infected, RF+: 30%	3.90%	7.60%
1	Pregnant infected	Non- pregnant infected	Risk difference for PASC in pregnant infected versus non- pregnant infected	Risk of PASC in non-pregnant infected: 25%	4.10%	8.00%
1	PASC+ w/ RF	PASC+ w/out RF	Difference in proportion who recover from PASC for those with and without a risk factor	Prevalence of RF: 20%, probability of recovery in PASC+ w/out RF: 0.50	8.70%	17.20%

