2	PASC+		Precision of rate of feature	Rate of 50% (conservative)	± 2.3%	± 4.7%
2	Infected	Uninfected	Difference in proportion with a features in between infected	Rate of 50% with feature in infected	7.90%	15.60%

			and uninfected individuals			
2	PASC+	PASC-	Difference in proportion with a feature, PASC+ vs. PASC-, infected only	Rate of 50% with feature in PASC+ (conservative)	10.00%	19.70%
3	PASC+		Precision of rate of feature	Rate of 50% (conservative)	± 2.8%	± 5.7%
3	Infected	Uninfected	Difference in proportion with a feature, infected vs. uninfected	Rate of 50% in PASC+ (conservative)	9.50%	18.80%
3	PASC+	PASC-	Difference in proportion with a feature, PASC+ vs. PASC-	Rate of 50% in PASC+ (conservative)	12.10%	23.40%

Only infected participants are included in analyses that consider PASC+ alone, or compare PASC+ with PASC-.

*ES: effect size; RF: risk factor

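### Table 7's infected-versus-uninfected detectable differences for Tiers 2 and 3 (7.9%, 9.5%) ignore the symptom-based sampling; for the cohort-level contrast they are about 9.7–12.0% and 11.7–14.6%

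*Protocol*

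**What the plan says.** The Protocol Summary sets the cohort at "12,200 total subjects with SARS-CoV-2 infection and 2,680 total subjects without SARS-CoV-2 infection". Section 12.2 then builds the deeper tiers from it:

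- Symptom share: "These sample sizes for Tier 2 and Tier 3 assume that 25% of infected subjects will have abnormal symptoms".
- Tier 2 infected: "all infected subjects with abnormal symptoms will progress to Tier 2 (N=3,050) and 5.6% of infected subjects without symptoms" (the latter given as 512).
- Tier 2 uninfected: "Among uninfected subjects, 26.8% (N=718) will progress to Tier 2".
- Tier 3 infected: "68% of infected subjects with abnormal symptoms will progress to Tier 3, and 3.8% of infected subjects without symptoms will progress to Tier 3". For the uninfected, 18.2% go to Tier 3.

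Section 8.1 adds that the random part of the uninfected sample is 11.4% of those without relevant symptoms. Section 6.1 sorts participants into four buckets by infection and symptom status and oversamples those with relevant symptoms, to obtain enough likely positive tests.

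The effect in the Tier 2 comparison row of Table 7 is worded "Difference in proportion with a features in between infected" and uninfected individuals, with no condition on symptoms. Its detectable difference is 7.90% (15.60% in a 25% subgroup). The Tier 3 counterpart is 9.50% (18.80%). Section 12.2 mentions no weighting, design effect or effective sample size, and gives neither alpha nor power.

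**The concern.** The infected Tier 2 sample is 3,050/3,562 = 86% symptomatic, against 25% in the infected cohort. The 512 symptom-free infected participants have to represent 9,150 people. A difference between infected and uninfected people as groups must give that stratum its 75% share, and its small size then dominates the variance. A formula that treats 3,562 as a simple random sample overstates the information available.

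What is at stake is the sensitivity claimed for the Tier 2 and Tier 3 infected-uninfected questions. The claim carries weight because Section 6.1 stops assigning a test in a bucket once the Section 12.2 target is met, and defends the resulting numbers: "This ensures that our total enrollment and procedure sample sizes are as small as can be in order to ensure usable data". Section 6.1 also justifies testing uninfected participants by the need for comparisons with controls.

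**Working it through.** **Inputs (Section 12.2 unless noted)**

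- Infected: 12,200, of whom 3,050 have symptoms and 9,150 do not.
- Tier 2: 3,050 + 0.056 × 9,150 = 3,050 + 512 = 3,562 infected; 718 uninfected.
- Tier 3: 0.68 × 3,050 + 0.038 × 9,150 = 2,074 + 348 = 2,422 infected; 0.182 × 2,680 = 488 uninfected.
- Feature rate: 50%. The Tier 3 row attaches this rate to PASC+; it is applied here to the infected.
- Alpha and power: not stated, so inferred in step 1.

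**Step 1. Reproduce the stated figures**

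A two-proportion test on raw counts, with pooled null variance, two-sided alpha 0.01 and 90% power, gives:

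| Row | Recomputed | Table 7 |
|---|---|---|
| Tier 2, full | 7.86% | 7.90% |
| Tier 2, 25% subgroup | 15.55% | 15.60% |
| Tier 3, full | 9.52% | 9.50% |
| Tier 3, 25% subgroup | 18.74% | 18.80% |
| Tier 1 infected v uninfected | 3.49% | 3.50% |

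Other settings do not fit. For Tier 2, alpha 0.05 gives 5.7% at 80% power and 6.6% at 90%; alpha 0.01 at 80% power gives 7.0%. The PASC+ precision of ±2.3% is also a 99% half-width: 2.576 × 0.5/√3,050 = 2.33% (a 95% half-width is 1.77%).

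**Step 2. Effective sample size of the infected**

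Weighted to the cohort, at a 50% rate in both strata:

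Var = 0.25² × 0.25/n(symptomatic) + 0.75² × 0.25/n(symptom-free), and n_eff = 0.25/Var.

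- Tier 2: 0.015625/3,050 + 0.140625/512 = 2.80 × 10⁻⁴, so n_eff ≈ 894 (design effect about 4.0).
- Tier 3: 0.015625/2,074 + 0.140625/348 = 4.12 × 10⁻⁴, so n_eff ≈ 607.

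**Step 3. The uninfected, two cases**

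- *Equal-probability sample:* 718 and 488.
- *Symptom-enriched:* assume all symptomatic uninfected enter Tier 2, plus 11.4% of the rest. Then x + 0.114(1 − x) = 0.268 gives x = 0.154/0.886 = 17.4% symptomatic, or 466 + 252 = 718 tested, with n_eff ≈ 361. For Tier 3, assume 68% of the symptomatic enter. The 18.2% overall then implies about 7.7% of the rest, or 317 + 171 = 488 tested, with n_eff ≈ 245.

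**Step 4. Detectable difference**

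d = (2.576 + 1.282) × √[0.25 × (1/n₁ + 1/n₂)]

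| | Infected weighted only | Both weighted |
|---|---|---|
| Tier 2 | 894 v 718: 9.7% | 894 v 361: 12.0% |
| Tier 3 | 607 v 488: 11.7% | 607 v 245: 14.6% |
| Tier 2, 25% subgroup | 19.3% | 24.1% |
| Tier 3, 25% subgroup | 23.5% | 29.2% |

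On raw counts this closed form gives 7.89% and 9.57%, so the choice of formula does not cause the gap. Power at the stated 7.9% and 9.5% falls from 90% to about 72% and 71% (infected weighted only), or about 48% in each tier (both weighted).

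**Step 5. Sensitivity to the 50% rate**

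With the feature in 50% to 90% of symptomatic people and 50% overall, Tier 2 runs 9.5–9.7% (infected weighted only) and 11.7–12.0% (both weighted). Tier 3 runs 11.5–11.7% and 14.2–14.6%.

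**Step 6. Difference conditional on symptom stratum**

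Pool Bucket 1 v 2 and Bucket 3 v 4 with information Σ n₁n₂/(n₁ + n₂), using the enriched counts from step 3:

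- Tier 2: 3,050 × 466/3,516 + 512 × 252/764 ≈ 404 + 169 = 573; d = 3.858 × 0.5/√573 ≈ 8.1%.
- Tier 3: 2,074 × 317/2,391 + 348 × 171/519 ≈ 275 + 115 = 390; d ≈ 9.8%.

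**The case against.** The best reply is that the design does not oblige anyone to weight. Section 6.1 assigns tests by bucket so that buckets can be told apart in analysis, and a contrast pooled within symptom strata detects about 8.1% and 9.8%, close to the table. This stands as far as it goes: the table is nearly right for that conditional quantity. But the conditional difference answers another question, and the rows name infected against uninfected without any condition.

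A reader might go further and infer that the Tier 2/3 analyses will be unweighted and therefore biased. The documents do not support that. Section 12.5 refers the complete analytic approach to the SAP, which is not at hand and may specify weighting. An unweighted contrast would mislead only for features linked to symptoms, and nothing in the protocol says one is planned.

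A reader might also infer that assignment probabilities are being lost, since Section 6.1 lets the proportions adapt. REDCap makes the assignments, the SOPs and MOP hold the details, and nothing says the probabilities are not kept.

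The inferred settings are a fair caution. The same alpha and power give about 9.2% and 11.1% for the PASC+ versus PASC- rows, against 10.0% and 12.1% in Table 7, so not every row fits. The four infected-uninfected figures in question do.

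**Conclusion.** The Tier 2 and Tier 3 infected-versus-uninfected entries are simple-random-sample figures and are too favourable for the contrast they describe. Under Section 12.2's own fractions the detectable differences are about 9.7–12.0% instead of 7.9%, and 11.7–14.6% instead of 9.5%, with subgroup values about twice as large.

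This rests on an inferred two-sided alpha of 0.01 and 90% power, and on a 50% feature rate. The lower ends take the uninfected as an equal-probability sample. The upper ends assume that all symptomatic uninfected enter Tier 2 and 68% enter Tier 3, with 17.4% symptomatic implied; the protocol does not state those uninfected fractions. If the SAP weights, that deals with bias but leaves the stated figures wrong, because weighting is what produces the larger values.

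This is a correction of stated sensitivity and not a flaw that must be cured before the study can proceed. The primary endpoint is symptom presence over time, which comes from Tier 1 data and is unaffected. Nor do the figures by themselves show that the allocation should change: moving tests towards symptom-free infected people is a trade-off in burden and in precision for PASC+.

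**What to change.** - In Table 7, replace the four infected-versus-uninfected values for Tiers 2 and 3 (full sample and 25% subgroup) with design-weighted ones, stating the uninfected sampling fractions by symptom status that they assume. Alternatively, relabel the rows as differences conditional on symptom stratum (Bucket 1 v 2 and 3 v 4 pooled) and give about 8.1% and 9.8%.
- State alpha, sidedness and power in Section 12.2.
- Confirm that wherever the SAP estimates an overall Tier 2 or Tier 3 infected-uninfected difference, it uses the assignment probabilities.

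The cost is a small text change and less favourable stated figures. No change to sampling, testing or enrolment is needed.

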8.1 Overview of Study Schedule

Data will be collected at baseline and then following the study schedule, which starts at time of first infection for those enrolled during first infection or after their first infection without an active infection at time of enrollment; at time of reinfection if enrolled during an acute infection; or at time of negative COVID-19 test, for those who are uninfected. Uninfected pregnant individuals will begin the study schedule on their delivery date. See **Table 3**. Collection will be tiered such that all enrolled patients will undergo Tier 1 data collection, and those with abnormal findings on Tier 1 collection may progress to more intensive, invasive, or costly Tier 2 and Tier 3 data collection. We anticipate that approximately 30% of participants will undergo each Tier 2 test and a maximum of 20% of enrollees will undergo each Tier 3 test for any given symptom, including both those with relevant symptoms and a random sample of 5.6% of SARS-CoV-2 infected and 11.4% of uninfected subjects without relevant symptoms. All patients will undergo at least one in-person visit annually, which can be provided at home if provisions are made for home blood and biospecimen collection.

Table 3: Index date and study schedule date, by enrollment type

Enrollment Category	Index Date	Study Schedule Start Date	
Acute Infected (First Infection)	First positive SARS-CoV-2 test	First positive SARS-CoV-2 test	
	result date or, if test not	result date or, if test not	

	available, date of COVID symptom onset	available, date of COVID symptom onset
Acute Infected (Reinfected)	First positive SARS-CoV-2 test result date or, if test not available, date of COVID symptom onset	Most recent positive SARS- CoV-2 test result date or, if test not available, date of COVID symptom onset
Acute Uninfected	Qualifying negative SARS-CoV-2 test result date	Qualifying negative SARS-CoV-2 test result date
Post-Acute Infected	First positive SARS-CoV-2 test result date or, if test not available, date of COVID symptom onset	First positive SARS-CoV-2 test result date or, if test not available, date of COVID symptom onset
Post-Acute Uninfected	Qualifying negative SARS-CoV-2 test result date. For pregnancy sites only , index date is the prior delivery date	Qualifying negative SARS-CoV-2 test result date. For pregnancy sites only , index date is the prior delivery date

Home Visits

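### Section 12.2's Tier 2 and Tier 3 totals do not match their own components, and the sampling fractions in Sections 6.1, 8.1 and 12.2 are not reconciled

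*Protocol*

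**What the plan says.** The Protocol Summary plans "12,200 total subjects with SARS-CoV-2 infection and 2,680 total subjects without SARS-CoV-2 infection", 14,880 in all. Section 12.2 introduces Table 7 as giving detectable effects for the full sample, "Tier 1 N=14,880; Tier 2 N=4,464 and Tier 3 N=2,976", and for 25% subgroups of it. It then builds the tiers up: "These sample sizes for Tier 2 and Tier 3 assume that 25% of infected subjects will have abnormal symptoms". For Tier 2 it takes all of those (3,050) and 5.6% of infected participants without symptoms (512). For the uninfected it says "Among uninfected subjects, 26.8% (N=718) will progress to Tier 2". For Tier 3 it takes 68% of symptomatic infected participants and 3.8% of the other infected participants, and adds: "Among uninfected subjects, 18.2% will progress to Tier 3".

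Two other sections give sampling fractions. Section 6.1 says of Tier 2 that "a random sample of 5.6% of SARS-CoV-2 infected and 11.4% of uninfected participants will be asked to undergo each Tier 2 test", with participants who meet clinical criteria added on top. Section 8.1 covers Tier 2 and Tier 3 in one sentence: those with relevant symptoms plus "a random sample of 5.6% of SARS-CoV-2 infected and 11.4% of uninfected subjects without relevant symptoms".

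Section 6.1 also sorts participants into four buckets by infection and symptom status. It stops assigning a test in a bucket once the Section 12.2 target for that bucket is reached with adequate data quality.

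**The concern.** Section 12.2 is the reference for the assignment system, so its numbers have a practical effect. There are three difficulties.

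- The totals are not the sum of the parts listed directly after them.
- Sections 8.1 and 12.2 give different Tier 3 random fractions for the same people, infected participants without symptoms.
- Nothing links the 11.4% random fraction for uninfected participants to the 26.8% of all uninfected participants counted in Section 12.2.

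The stopping rule works by bucket. Section 12.2 separates infected participants by symptoms but gives uninfected participants only as one pooled figure per tier. Buckets 2 and 4 (uninfected with and without relevant symptoms) therefore have no target of their own. If the control group falls short, the infected-versus-uninfected comparisons lose the precision that Table 7 states.

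**Working it through.** **1. Totals.** Inputs are from the Protocol Summary and Section 12.2: 12,200 infected (3,050 with symptoms, 9,150 without) and 2,680 uninfected.

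| | Infected, symptoms | Infected, no symptoms | Uninfected | Sum | Stated |
|---|---|---|---|---|---|
| Tier 2 | 3,050 | 0.056 × 9,150 = 512 | 0.268 × 2,680 = 718 | 4,280 (28.8% of 14,880) | 4,464 |
| Tier 3 | 0.68 × 3,050 = 2,074 | 0.038 × 9,150 = 348 | 0.182 × 2,680 = 488 | 2,910 (19.6%) | 2,976 |

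The shortfalls are 184 and 66. The stated totals are exactly 0.30 × 14,880 and 0.20 × 14,880, the planning shares in Section 6.1.

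**2. Which numbers lie behind Table 7.** Section 12.2 states neither alpha nor power. The precision rows point to a two-sided alpha of 0.01: 2.576 × 0.5/√3,050 = 2.3% and 2.576 × 0.5/√2,074 = 2.8%, as stated. The detectable difference D then solves

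D = 2.576 √[p̄(1−p̄)(1/n₁+1/n₂)] + 1.282 √[p₁(1−p₁)/n₁ + p₂(1−p₂)/n₂],

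with p₁ = 0.50, p₂ = 0.50 − D, p̄ the weighted mean, and 90% power.

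- Tier 2, 3,562 v 718: 0.0527 + 0.0259 = 7.86% (stated 7.9%). 25% subgroup: 15.55% (stated 15.6%).
- Tier 3, 2,422 v 488: 9.52% (stated 9.5%). 25% subgroup: 18.73% (stated 18.8%).
- Totals reached by adding controls: 4,464 − 3,562 = 902 and 2,976 − 2,422 = 554. These give 7.2% and 9.0%.
- Totals reached by scaling both groups in proportion: 3,715 v 749 and 2,477 v 499. These give 7.7% and 9.4%.

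Only the components reproduce the stated figures. The PASC+ versus PASC− rows (10.0% and 12.1%) do not reproduce at these settings (9.2% and 11.1%), and nothing here rests on them.

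**3. Tier 3 random fraction.** Within Section 12.2, the Tier 3 fractions are 0.68 times the Tier 2 ones: 0.68 × 5.6% = 3.8% and 0.68 × 26.8% = 18.2%. Section 8.1's 5.6% would give 512 infected participants without symptoms, not 348. The Tier 3 sum would then be 2,074 + 512 + 488 = 3,074, or 20.7% of 14,880, above the 20% maximum in Sections 6.1 and 8.1.

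**4. Linking 11.4% to 26.8%.** Let x be the share of uninfected participants with the relevant symptom, all of them assigned. The number tested is 2,680 × [x + 0.114(1 − x)]. Setting this equal to 0.268 × 2,680 gives x = (0.268 − 0.114)/(1 − 0.114) = 17.4%. With infected participants held at 3,562 and the rates left unadjusted:

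| x (assumed) | Uninfected tested | Tier 2 detectable difference |
|---|---|---|
| 0% | 306 | 11.4% |
| 5% | 424 | 9.8% |
| 10% | 543 | 8.8% |
| 17.4% | 718 | 7.9% |
| 20% | 780 | 7.6% |

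The protocol states no value of x. Appendix 5 sets different triggers for each test, for example altered smell or taste for UPSIT, and liver enzymes or the FIB-4 index for Fibroscan. One share is therefore unlikely to hold for every test.

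**The case against.** A reader might infer that the 11.4% rate yields only 306 uninfected controls in place of 718, so that the 7.9% should read 11.4% (22.3% in the subgroup, reading the components the same way) with power of about 53% at 7.9%. The documents do not support this. The 11.4% is only the random part, and Section 8.1 limits it to uninfected participants without relevant symptoms. Section 6.1 makes symptomatic uninfected participants a separate source (Bucket 2), and many triggers, such as fatigue, cough and palpitations, are not specific to infection. Section 6.1 also lets the percentages change as testing accrues. So 306 is a floor that requires no uninfected participant to have a relevant symptom. Setting 11.4% against the Tier 3 figure of 18.2% likewise compares a part with a whole.

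A reader might also discount Table 7 for refusals, because the Section 6.1 ceiling is on assignment ("keep the total number of participants assigned to the test at not more than 30" per cent) and any test may be declined. Asking how refusals are covered is fair, but the protocol gives no uptake rate. Any loss calculated from an assumed rate is a scenario, not an error in the plan.

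It is also fair to say that 4,464 and 2,976 are rounded planning shares, and that correcting them changes neither infected-versus-uninfected row. That limits the consequence. It does not make the totals right, because Section 12.2 presents them as the sample sizes behind Table 7 and as the result of the listed assumptions. Section 8.1's Tier 3 fraction may be compressed drafting, but as written no symptomatic share reconciles 5.6% with 3.8% for the same group.

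**Conclusion.** The point holds as an internal inconsistency in the sample-size section and its cross-references. The Tier 2 total is overstated by 184 (4.1% of 4,464) and the Tier 3 total by 66 (2.2% of 2,976). The Tier 3 random fraction for infected participants without symptoms differs by 164 people between Sections 8.1 and 12.2.

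The infected-versus-uninfected rows of Table 7 are sound for the component counts. Reaching 718 Tier 2 controls at the stated random rate depends on an unstated symptomatic share of about 17.4% with full assignment, or on later adjustment of the rates. A smaller share without adjustment would raise the detectable difference to somewhere between 7.9% and the 11.4% floor. These figures rest on the inferred alpha of 0.01 and power of 90%. The documents do not show that the design as written yields too few controls.

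**What to change.** 1. In Section 12.2, correct the totals to 4,280 and 2,910, and describe 30% and 20% as planning ceilings, not as the sample sizes behind Table 7.
2. Give the same Tier 3 random fractions in Sections 8.1 and 12.2, or limit the Section 8.1 fractions to Tier 2.
3. Split the uninfected targets of 718 (Tier 2) and 488 (Tier 3) into symptomatic (Bucket 2) and asymptomatic (Bucket 4) numbers and state the symptomatic share assumed. The Section 6.1 stopping rule then works towards the counts behind Table 7. Use one denominator for the 11.4%: Section 6.1 words it as uninfected participants, Section 8.1 as those without relevant symptoms.

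The Tier 2 row should not be restated as 11.4%/22.3%, which would leave out Bucket 2.

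The cost is protocol wording and a REDCap parameter. The stated totals become slightly smaller, and no new recruitment is needed.

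### Table 7: the two PASC+ vs PASC- rows do not follow from the section 12.2 counts on the standard that fits the other eight rows

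*Protocol*

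**What the plan says.** Section 12.2 of the protocol says that "Table 7 shows minimal detectable effect sizes for the key study questions", for the full sample and for 25% subgroups. The inputs are in the same section and in the Protocol Summary:

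- There are 12,200 infected and 2,680 uninfected participants. The tier sizes "assume that 25% of infected subjects will have abnormal symptoms", which is 3,050 with symptoms and 9,150 without.
- Tier 2 takes all 3,050 symptomatic infected participants, 512 of the infected without symptoms (5.6%) and 718 of the uninfected (26.8%).
- For Tier 3, "68% of infected subjects with abnormal symptoms will progress to Tier 3, and 3.8% of infected subjects without symptoms will progress to Tier 3", together with 18.2% of the uninfected.
- The stated tier totals are 4,464 and 2,976.

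Table 7 then prints 10.0%/19.7% for the Tier 2 row "Difference in proportion with a feature, PASC+ vs. PASC-, infected only" and 12.1%/23.4% for its Tier 3 counterpart, both with a 50% rate in PASC+. The infected-vs-uninfected rows are 7.9%/15.6% (Tier 2) and 9.5%/18.8% (Tier 3), also at a 50% reference rate. A note under the table confines the PASC+ vs PASC- comparisons to infected participants. Nothing says that these two rows use a different standard from the rest.

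**The concern.** Table 7 is the protocol's statement of what the study can detect, and PASC+ vs PASC- is one of its key comparisons. A reader will assume that all rows share one error rate and one power and that they come from the counts printed above them. If two rows do not, the rows cannot be compared with one another, and either the effect sizes or the counts are wrong.

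The stake is the accuracy of the stated sensitivity. An alpha or power given in a separate analysis plan cannot settle the matter if it is common to all rows, because the conflict between rows of the same tier remains whatever common values are used.

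**Working it through.** **Inputs.** Symptomatic infected are taken as PASC+ and infected without symptoms as PASC-. Tier 2: PASC+ 3,050; PASC- 512; infected 3,050 + 512 = 3,562; uninfected 718. Tier 3: PASC+ 0.68 × 3,050 = 2,074; PASC- 0.038 × 9,150 = 348; infected 2,074 + 348 = 2,422; uninfected 0.182 × 2,680 = 488. Subgroups use one quarter of each.

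**Formula.** The detectable difference d solves

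d = z(1−α/2) × √[p̄(1−p̄)(1/n1 + 1/n2)] + z(power) × √[p1(1−p1)/n1 + p2(1−p2)/n2],

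with p2 = p1 − d and p̄ = (n1p1 + n2p2)/(n1 + n2). Precision rows use z × √(0.25/n).

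**Step 1: reproduce the other eight rows.** Table 7 prints no alpha or power, so both were found by fitting. Two-sided alpha 0.01 (z = 2.576), 90% power (z = 1.282) and 99% intervals give:

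| Row | Computed (full/subgroup, %) | Printed |
|---|---|---|
| Tier 1 infected (12,200) vs uninfected (2,680) | 3.49/6.84 | 3.5/6.8 |
| Tier 1 risk factor (2,440 vs 9,760) | 3.90/7.59 | 3.9/7.6 |
| Tier 1 pregnant (1,867 vs 10,333) | 4.10/8.00 | 4.1/8.0 |
| Tier 1 recovery (610 vs 2,440) | 8.69/17.15 | 8.7/17.2 |
| Tier 2 infected vs uninfected | 7.86/15.55 | 7.9/15.6 |
| Tier 3 infected vs uninfected | 9.52/18.73 | 9.5/18.8 |
| Tier 2 precision (3,050) | ±2.33/4.66 | ±2.3/4.7 |
| Tier 3 precision (2,074) | ±2.83/5.66 | ±2.8/5.7 |

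The first three rows fit with the uninfected, the group without the risk factor and the pregnant group, respectively, taken as the lower-risk group. Every cell agrees to within 0.1 point. The precision rows would be ±1.77/3.55 and ±2.15/4.30 at 95% confidence, so 99% is clear.

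**Step 2: the two PASC+ vs PASC- rows on the same settings.**

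- Tier 2, 3,050 vs 512: 2.576 × 0.02387 + 1.282 × 0.02353 = 0.0615 + 0.0302, or 9.16% before rounding of the terms. Subgroup 18.05%. Printed: 10.0% and 19.7%.
- Tier 3, 2,074 vs 348: 2.576 × 0.02895 + 1.282 × 0.02835 = 0.0746 + 0.0363, or 11.09%. Subgroup 21.69%. Printed: 12.1% and 23.4%.

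Excess of printed over computed: 0.84 and 1.01 points (full sample), 1.65 and 1.71 points (subgroup).

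**Step 3: a check that assumes no particular alpha or power.** Within a tier both comparisons use a 50% reference rate, so at any common alpha and power the ratio of their detectable differences is close to the ratio of √(1/n1 + 1/n2):

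- Tier 2: √(0.002281/0.001673) = 1.17. Printed: 10.0/7.9 = 1.27.
- Tier 3: √(0.003356/0.002462) = 1.17. Printed: 12.1/9.5 = 1.27.

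The full formula gives 1.16 to 1.17 for the full sample across alpha 0.05, 0.01 and 0.001 and power 80%, 90% and 95%. Rounding does not close the gap: the smallest ratios compatible with the printed figures are 9.95/7.95 = 1.25 and 12.05/9.55 = 1.26.

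**Step 4: candidate explanations for the two rows.**

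| Change from the common standard | Tier 2 (printed 10.0/19.7) | Tier 3 (printed 12.1/23.4) |
|---|---|---|
| 95% power | 10.01/19.60 | 12.10/23.47 |
| alpha 0.01/3, 90% power | 10.01/19.70 | 12.11/23.64 |
| PASC- about 416 and 286, 90% power | 10.02/19.67 | 12.06/23.41 (subgroup counts in whole people) |

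All three come close, so the figures do not identify the cause. A change of variance formula does not help: unpooled, continuity-corrected and arcsine versions at 90% power stay within 9.08–9.28% and 10.95–11.26%.

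**Step 5: the counts against the tier totals.** Tier 2: 3,050 + 512 + 718 = 4,280, stated 4,464. Tier 3: 2,074 + 348 + 488 = 2,910, stated 2,976. Adding the missing 184 or 66 people to PASC- would lower the detectable difference, so the shortfall does not explain the two rows. It does show that the counts need checking too.

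**The case against.** The strongest reply is that every benchmark here is back-solved, since the protocol leaves analytic detail to a separate plan; that the printed values err on the safe side; and that no analysis depends on them. Much of this stands. Alpha 0.01 and 90% power are inferred, and their absence from the protocol is not itself a fault. The discrepancy is small and conservative. What it does not answer is the ratio in step 3, which no common alpha or power repairs.

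Two stronger readings are tempting and are not supported:

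- **That the table mixes 90% and 95% power.** 95% power fits the full-sample cells but misses both subgroup cells by 0.1 point (19.6 and 23.5 against 19.7 and 23.4). A stricter alpha or smaller PASC- counts fit about as well. What is shown is a mismatch between the rows and the counts, not its cause.
- **That asymptomatic infected participants (Bucket 3) are over-tested.** A reader might note that 10.0% and 12.1% need only about 418 and 284 of them at 90% power, and infer an excess of 94 and 64 people per test. But section 6.1 says: "Once the target sample size (see Section 12.2) has been reached with adequate data quality within each bucket, we cease assigning the test". That rule acts on a target count. Section 12.2 fixes the counts by percentages and reports detectable differences for them, so a misprinted difference changes no quota. The same group also contributes to the infected-vs-uninfected comparison and to the search for subclinical change that section 6.1 describes.

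**Conclusion.** The two PASC+ vs PASC- rows are wrong as written: they and the section 12.2 counts cannot both be right on the standard used elsewhere in Table 7. If the counts and that standard are intended, the rows should read about 9.2%/18.1% (Tier 2) and 11.1%/21.7% (Tier 3). The study's sensitivity is then understated, so this is no sign of an underpowered comparison, and no conclusion is put at risk.

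The corrected values rest on three assumptions: symptomatic infected participants are PASC+ (supported by the precision rows, which reproduce with 3,050 and 2,074); the reference rate is 50% in the infected for the Tier 3 infected-vs-uninfected row, although its label names PASC+; and the common standard is the inferred one. The inconsistency itself rests only on the first two.

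**What to change.** Find the calculation behind the two rows and reconcile it with section 12.2, then do one of the following:

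- If the counts and the common standard are intended, restate the rows as 9.2%/18.1% and 11.1%/21.7%.
- If other PASC- counts were used, correct the counts in section 12.2.
- If a different power or alpha was meant for these rows, label it in the table.

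In the same edit, make the Tier 2 and Tier 3 components agree with their totals (4,280 vs 4,464; 2,910 vs 2,976), and state the common alpha, power and confidence level in the Table 7 footnote. Leave the Bucket 3 quotas as they are; this discrepancy gives no ground for changing them. The cost is two table rows, a footnote and a check of the counts.
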